#### 4.3 Sample size

The primary objective is descriptive. Formal sample size calculations were therefore not performed. We estimated to be able to see 500-700 women in one year with the funding we received from EDCTP. However, our estimate may have been conservative, in which case the sample size may be increased to up to 1,000 women. Based on prevalence data from recent RU studies in the same high risk population, if we see 500 clients (assuming that they do not opt out of any services offered), we expect to diagnose 100 cases of HIV, 35 cases of syphilis, 60 cases of NG, 75 cases of CT, 75 cases of TV, 175 cases of BV, 50 cases of vaginal candidiasis, and 115 cases of UTI.

Data for the qualitative research objectives will be gathered at two workshops with stakeholders: one to be held before initiation of the study and one after completion of the study. In addition, IDIs will be done with clinicians, programme implementers and policymakers. The number of IDIs to be held will be governed by data saturation: no new interviews will be done when they no longer generate new information. We expect to conduct approximately 10 IDIs.

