- The Rwandan VDS algorithms incorporate a predetermined set of questions for CT/NG risk scoring, as well as CT/NG treatment when a woman's partner has urethritis complaints. The WHO guidelines do provide the possibility for risk scoring but state that risk scoring should be guided by local epidemiology. *In this SAP, when evaluating the performance of the Rwandan guidelines, we will follow the Rwandan risk scoring as outlined in the algorithm.* One of the possible risk factors in the Rwandan guidelines is "2 or more sexual partners" but no time frame is given; we will use 2 or more sexual partners in the past 12 months. When evaluating the performance of the WHO guidelines, we will assume high risk for CT/NG based on the local epidemics in our research communities.
- In the Rwandan VDS algorithms, candidiasis is diagnosed based on the presence of unusual vaginal discharge and a low CT/NG risk score, while in the WHO guidelines candidiasis is only treated in the presence of typical signs and symptoms (vulval oedema/curd-like discharge, vulval erythema or excoriations). *In this SAP, we will follow each respective guideline when evaluating the performance of that guideline.*
- In the Rwandan algorithms, all female sex workers (FSWs) without symptoms are to receive presumptive treatment for NG, CT and TV. However, when they do report symptoms, the usual syndromic algorithms are to be used and no presumptive treatment should be given. No definition of FSW is given. In this SAP, we will define sex work by self-reported exchange of sex for money and/or goods in the past 12 months, and we will follow the Rwandan guidelines.

Flow diagrams of the WISH algorithms, as described in section 1.3, are shown in appendix 8.3.

2. Participant disposition

The number of participants was dictated by the available budget and no formal statistical power calculations were performed. 705 participants were enrolled in the study.

² World Health Organization, 2008: Report of the Expert Consultation and Review of the Latest Evidence to Update Guidelines for the Management of Sexually Transmitted Infections.

³ Republic of Rwanda – Ministry of Health, 2010: National Guide on the Care of Sexually Transmitted Infections – Manual of the Care Provider.

⁴ Republic of Rwanda – Ministry of Health, 2013: National Guidelines for Prevention and Management of HIV, STIS & Other Blood Borne Infections.

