All women were risk-scored for CT/NG and syphilis. Each of the two risk scores consisted of four questions based on the face-to-face interview and findings during speculum and bimanual examination (if applicable). GeneXpert CT/NG testing was only offered if the participant was positive for the CT/NG risk score and syphilis testing was only offered if the participant was positive for the syphilis risk score. However, a sample for GeneXpert testing was taken from all participants (a vaginal sample with the option of a urine sample if the participant refused vaginal sampling) so that we would have a CT/NG GeneXpert result for all participants at the end of the study. Participants who had a negative CT/NG risk-score but tested positive on the GeneXpert later on in the study were contacted for treatment at an Additional Visit.

CT/NG risk score	n (%) N = 705
Currently pregnant	
Exchanged sex for money or goods in the past 12 months	
New sex partner in the past three months	
Abnormal cervicovaginal discharge during speculum exam and/or cervical motion/adnexal tenderness during bimanual exam (if pelvic/bimanual not done, the answer was no)	
Final CT/NG risk score ¹ : - Positive	
- Negative	
Syphilis risk score	n (%)
Currently pregnant	
Exchanged sex for money or goods in the past 12 months	
New sex partner in the past three months	
Genital ulcers/blisters/sores visible during pelvic exam (if pelvic/bimanual not done, the	
answer was no)	
Final syphilis risk score ¹ : - Positive	
- Negative	

Abbreviations: CT = *Chlamydia trachomatis*; NG = *Neisseria gonorrhoeae*.

1. The risk score was positive if at least one of the four criteria was positive. If a speculum/bimanual examination was not done, the answer was no for that question.

Urogenital symptoms reported spontaneously and after structured questioning at Main Visits: During the face-to-face interview, participants were asked the following two questions in the order given:

- "Do you experience, or did you experience in the past 2 weeks, any urogenital symptoms?" We

will refer to these as *spontaneously reported symptoms*.

- "Do you experience, or did you experience in the past 2 weeks, any of the urogenital symptoms below?", followed by a list of symptoms that were read out loud to the participant. We will refer to these as *structurally reported symptoms*.

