5.3 Comparisons syndromic management vs. WISH procedures vs. gold standard testing In this section, all hypothetical syndromic management (under WHO guidelines) individual algorithms and presumed treatments of STIs will be compared to the POCT results as performed during the WISH study, and to the gold standard results. For each outcome, sensitivity, specificity, positive predictive value (PPV) and negative predictive value (NPV) will be reported (see next page).

Procedure 1	Procedure 2	N pos/pos	N pos/neg	N neg/pos	N neg/neg	OR (95% CI) ¹	Sens. ²	Spec. ²	PPV ²	NPV ²
	(reference)	(= TP)	(= FP)	(= FN)	(= TN)	Fisher's p	(%)	(%)	(%)	(%)
Syndromic (WHO)	WISH procedures									
Any VDS (with or without LAP,	CT/NG (after RS) ³ by POCT, TV/BV						_			
typical or not for candidiasis)	by POCT, or treated for candidiasis								 	
Any VDS (with or without LAP,	CT/NG (after RS) ³ by POCT, TV/BV									
typical or not for candidiasis)	by POCT								 	
Any VDS (with or without LAP,	CT/NG (after RS) ³ by POCT									
typical or not for candidiasis)									L	
Any VDS (with or without LAP,	CT (after RS) ³ by POCT						_			
typical or not for candidiasis)									L	
Any VDS (with or without LAP,	NG (after RS) ³ by POCT						_			
typical or not for candidiasis)									 	
Any VDS (with or without LAP,	TV/BV by POCT						_			
typical or not for candidiasis)									 	
VDS (with or without LAP, typical	Treated for candidiasis									
for candidiasis)									 	
PID (with or without VDS, after	CT/NG (after RS) ³ by POCT, TV/BV									
LAP)	by POCT								Ļ	
PID (with or without VDS, after	CT/NG (after RS) ³ by POCT									
LAP)									Ļ	
PID (with or without VDS, after	TV/BV by POCT						_			
LAP)									Ļ	
GUD	Syphilis algorithm (after RS) ⁴						-			
									Ļ	
Would have received treatment	CT/NG (after RS) ³ by POCT									
for CT/NG ⁵									Ļ	
Would have received treatment	TV/BV by POCT								ł	
for TV/BV ⁵									ł	

Procedure 1	Procedure 2	N pos/pos	N pos/neg	N neg/pos	N neg/neg	OR (95% CI) ¹	Sens. ²	Spec. ²	PPV ²	NPV ²
	(reference)	(= TP)	(= FP)	(= FN)	(= TN)	Fisher's p				
Syndromic (WHO)	Gold standard	-		_				-		-
Any VDS (with or without LAP,	CT/NG (on everyone) by POCT, or									
typical or not for candidiasis)	TV/BV ⁶ /CA by qPCR									
Any VDS (with or without LAP,	CT/NG (on everyone) by POCT, or									
typical or not for candidiasis)	TV/BV ⁶ by qPCR									

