- 2. As calculated by: sensitivity = TP / (TP + FN); specificity = TN / (TN + FP); positive predictive value = TP / (TP + FP); negative predictive value = TN / (TN + FN).
- 3. GeneXpert CT/NG testing was only offered if the participant was positive for the CT/NG risk score. The risk score was positive if at least one of the four following criteria was positive: 1) participant is currently pregnant 2) exchanged sex for money and/or goods in the past 12 months 3) reported a new sex partner in the last 3 months 4) abnormal cervicovaginal discharge during speculum exam and/or cervical motion/adnexal tenderness during bimanual exam. If a speculum/bimanual examination was not done, the last criterion was considered negative.
- 4. Syphilis testing was only offered if the participant was positive for the syphilis risk score. The risk score was positive if at least one of the four following criteria was positive: 1) participant is currently pregnant 2) exchanged sex for money and/or goods in the past 12 months 3) reported a new sex partner in the last 3 months 4) genital ulcers/blisters/sores visible during pelvic exam. If a pelvic examination was not done, the last criterion was considered negative.
- 5. Participant would have been received treatment covering CT/NG/TV/BV if she is positive for VDS (with or without LAP) and/or PID under the WHO guidelines. In the case of VDS, this is assuming all of our participants are at risk of CT/NG infection due to high local prevalence.
- 6. Further explained in the article by Jespers V, Crucitti T, [name] J et al. "A DNA tool for early detection of vaginal dysbiosis in African women." Res Microb 167.2 (2016): 133-41.

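### SAP 5.3: fifteen syndromic-versus-WISH rows use risk-score-restricted CT/NG testing as the reference; in the sex-worker and PID rows the index largely decides who is tested, so the accuracy figures, OR and p lean towards an association

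*SAP*

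**What the plan says.** The introduction to SAP 5.3 states that syndromic algorithms and "presumed treatments of STIs will be compared to the POCT results as performed during the WISH study", and also to gold-standard results. Procedure 2 is headed as the reference. The cells are labelled TP, FP, FN and TN, and each row carries an OR, Fisher's p, sensitivity, specificity, PPV and NPV.

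In the WISH-procedures blocks the CT/NG reference is the point-of-care result after risk scoring. Footnote 3 explains that "GeneXpert CT/NG testing was only offered if the participant was positive for the CT/NG risk score". The score is positive if any one of four items is present: pregnancy, sex exchanged for money or goods in 12 months, a new partner in 3 months, or "abnormal cervicovaginal discharge during speculum exam and/or cervical motion/adnexal tenderness during bimanual exam".

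For the sex-worker index, SAP 1.4 says: "In this SAP, we will define sex work by self-reported exchange of sex for money and/or goods in the past 12 months". The PID index (SAP 5.2, footnote 2) is lower abdominal pain with cervical motion, uterine or adnexal tenderness.

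Under risk scoring, SAP 4.1 records that "a sample for GeneXpert testing was taken from all participants", so that everyone would have a GeneXpert result by the end of the study. SAP 1.1, 4.2 and 5.4 treat GeneXpert on everyone as the gold standard. The last block of 5.3 evaluates risk-scored testing against that standard.

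**The concern.** The same variable, CT/NG after risk scoring, is the test under evaluation in the last block of 5.3 and the reference in fifteen other rows. As a reference it misses every infection in a score-negative woman. That is more than random incompleteness wherever the syndromic index also determines who scores positive. In those rows infections are looked for fully among index-positive women and only partly among the rest, and the table can then show an association that comes from the testing rule alone.

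Sensitivity, specificity, PPV and NPV are declared secondary endpoints, so a reader will take these rows as diagnostic accuracy. For a few indices no equivalent gold-standard row is printed beside them.

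**Working it through.** **Rows affected.** Counting the rows of the 5.3 table whose reference is or includes CT, NG or CT/NG after risk scoring:

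| Index | WHO | Rwandan | Link between index and WISH score |
|---|---|---|---|
| Asymptomatic sex worker | – | 3 | Same self-report as score item 2 |
| PID | 2 | – | Nearly the tenderness part of item 4 (uterine tenderness is extra) |
| Would have received CT/NG treatment | 1 | 1 | Partly, through PID and (Rwandan) sex work |
| VDS with positive Rwandan score | – | 2 | Shares new partner, one of four Rwandan items |
| Any reported VDS | 5 | 1 | Indirect, through examination findings |
| Total | 8 | 7 | |

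Nine rows have a CT and/or NG reference only. Six are composites with TV/BV, two of which also include candidiasis treatment.

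**Coding of untested women.** The SAP does not state it. The N = 705 tables and the WISH-versus-gold-standard rows imply negative, and that is assumed here. If they were excluded instead, sensitivity would be the same, but specificity and NPV would be lower than under negative coding.

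**Inputs.** There is no planned figure to reproduce, since "no formal statistical power calculations were performed". N = 705 (SAP section 2: "705 participants were enrolled in the study"). Protocol 4.3 expects, per 500 women, "60 cases of NG, 75 cases of CT", so NG = 60/500 = 12% and CT = 75/500 = 15%. Assumed, not in the documents: index share f = 15%; no true association; a share r of infected index-negative women who score positive.

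**Sex-worker rows.** Every index-positive woman scores positive. With prevalence p:

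- TP = N·f·p and FP = N·f·(1−p), both unchanged
- FN = N·(1−f)·p·r and TN = N·(1−f)·(1−p·r)
- Sensitivity = f/[f+(1−f)r]; NPV = 1−p·r; OR = (1−p·r)/[r(1−p)]

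For CT with r = 0.3: TP 15.9 and FP 89.9. FN falls from 89.9 to 27.0 and TN rises from 509.4 to 572.3.

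- Sensitivity, CT or NG: r = 0.3 gives 0.15/0.405 = 37%; r = 0.6 gives 0.15/0.66 = 23%; everyone tested gives 15%.
- OR, CT: 0.955/0.255 = 3.7; 0.91/0.51 = 1.8; everyone tested 1. At r = 0.9, 0.865/0.765 = 1.13.
- OR, NG: 0.964/0.264 = 3.7; 0.928/0.528 = 1.8. At r = 0.9, 0.892/0.792 = 1.13.
- NPV, CT: 95.5% to 91% instead of 85%. NG: 96.4% to 92.8% instead of 88%.
- PPV is unchanged; specificity rises slightly.

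Simulated Fisher p<0.05 with no true association occurs in about 93% to 42% of studies for CT and 89% to 34% for NG (r = 0.3 to 0.6). At r = 0.9 it is about 5% to 7%. With everyone tested it is about 4% to 5%.

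**Sex-worker composite row.** Assume CT/NG 20%, BV 35%, TV 15%, independence and r = 0.45.

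- Reference-positive, index-positive women: 1 − 0.80×0.65×0.85 = 55.8%
- Reference-positive, index-negative women: 1 − 0.91×0.65×0.85 = 49.7%
- OR is 1.28, sensitivity 16.5% instead of 15%, and rejection about 20%.

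**Reported-VDS rows.** Assume index share 40%, prevalence 20%, and shares r1 and r0 of infected women with and without VDS who score positive. PPV = p·r1, NPV = 1−p·r0, sensitivity = 0.4·r1/(0.4·r1+0.6·r0).

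- r1 = r0 = 0.5: PPV 10% instead of 20%, NPV 90% instead of 80%, sensitivity still 40%, OR still 1.
- r1 = 0.7, r0 = 0.5: sensitivity 0.28/0.58 = 48%, PPV 14%, NPV 90%, OR (0.14/0.86)/(0.10/0.90) = 1.47, rejection about 35%.

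**The case against.** The comparison itself is planned. Protocol 4.2 lists syndromic management against risk scoring followed by testing, with these same four measures, and SAP 1.1 repeats it. As a cross-table of two care procedures it is legitimate. This stands, and it is why the rows should be kept.

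The SAP also supplies much of the answer. Section 5.4 uses GeneXpert on everyone for CT and NG. Both CT/NG treatment rows and the three WHO VDS rows against CT/NG, CT and NG have exact gold-standard counterparts. WISH-treated PID is compared with the gold standard as a composite. This stands for most indices. The two syndromic WHO PID rows, however, have no syndromic gold-standard counterpart, and sex worker against CT and against NG have only a combined CT/NG one.

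The size may be small. Protocol 4.1 says the score would be built from the behaviours most strongly associated with these infections. Symptomatic sex workers, who are index-negative, also all score positive. Both push r upwards. This stands, and the share is unknown, so the range must include r = 0.9.

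A reader might infer that the score contains the index in all fifteen rows. The documents do not support that. SAP 1.4 defines VDS for these analyses without a speculum examination, whereas item 4 is discharge seen at one. New partner is only one of four Rwandan items, of which two are needed.

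**Conclusion.** The point holds in a limited form. Fifteen rows label cells as true or false against a reference that misses infections the study itself detects. The distortion has a predictable upward direction in sensitivity, NPV and OR in the three sex-worker rows and, almost as fully, in the two WHO PID rows. The two treatment rows inherit part of it, and the two Rwandan score-positive VDS rows share one item. In the six reported-VDS rows PPV falls and NPV rises, while sensitivity and OR need not move. In the composites the effect is diluted.

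The size rests on assumptions about the share of asymptomatic sex workers and about how often infected other women score positive. It runs from large (OR about 3.7 at 30%) to negligible (about 1.13 at 90%). No decision in the plan depends on Fisher's p, and the primary objective is descriptive. The consequence is misread secondary tables.

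It is also tempting to conclude that the reference should be replaced in all fifteen rows. That would remove a planned comparison, duplicate five existing rows, and leave the six composites with a reference that is neither the WISH procedure nor the gold standard.

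**What to change.** 1. Add four gold-standard rows to 5.3: syndromic PID against CT/NG on everyone; syndromic PID against CT/NG on everyone plus TV/BV by qPCR; asymptomatic sex worker against CT on everyone; and the same against NG on everyone.
2. Keep the syndromic-versus-WISH cross-tables, but present them as agreement between procedures, without TP/FP/FN/TN labels, OR or Fisher's p. If the protocol's sensitivity, specificity, PPV and NPV are retained, label them as relative to WISH procedures and not as diagnostic accuracy.
3. State that women not tested at the visit are coded negative in these rows.
4. Give the two rows comparing genital ulcer disease with syphilis after risk scoring the same label; they have the same structure.

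The cost is a few extra table rows and some relabelling. The added rows use results already planned, so no new testing is needed.

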5.4 Overview syndromic management and WISH procedures vs. gold standard testing

An overview table will be made to compare WHO and Rwandan syndromic management, and the procedures of the WISH study, with gold standard testing.

Abbreviations: BV = bacterial vaginosis; CT = Chlamydia trachomatis; FN = false negative; FP = false positive; FSW = female sex worker; GUD = genital ulcer disease; LAP = lower abdominal pain; NA = not applicable; NG = Neisseria gonorrhoeae; PID = pelvic inflammatory disease; POCT = point of care test; Sens. = sensitivity; Spec. = specificity; TN = true negative; TP = true-positive; TV = Trichomonas vaginalis; UTI = urinary tract infection; VDS = vaginal discharge syndrome.

1. Compared to gold standard testing (CT, NG, TV, BV, candidiasis) or WISH procedures reference test (Syphilis, UTI). Sensitivity calculated by TP / (TP + FN); specificity calculated by TN / (TN + FP).

2. Under WHO syndromic management, the participant is treated for CT/NG if she is positive for VDS (with or without LAP) and/or PID. Under Rwandan syndromic management, the participant is treated for CT/NG if she is positive for VDS and (one of) her partner(s) has urethritis or she is positive for a risk score (2 or more positive of: age < 21; being single; 2 or more sexual partners in the past 12 months; new sexual partner in the last 3 months), if she has PID, or if she is an asymptomatic FSW. Under WISH procedures, the participant is offered GeneXpert CT/NG POCT testing if she is positive for the WISH CT/NG risk score previously described, and treated based on the test results. Gold standard is defined as GeneXpert CT/NG POCT performed on everyone.

3. Under WHO syndromic management, the participant is treated for BV/TV if she is positive for VDS (with or without LAP) and/or PID. Under Rwandan syndromic management, the participant is treated for BV/TV is she is positive for VDS (no matter the Rwandan CT/NG risk score described under (2)), if she has PID, or if she is an asymptomatic FSW. Under WISH procedures, the participant is offered TV OSOM POCT testing and treated based on the test results, and is offered BV by pH testing and treated based on the test results (a pH of 5.0 or higher is treated, regardless of symptoms). Gold standard testing is defined as TV qPCR, and BV qPCR vaginal health score, as explained in section 5.1

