The following table describes, per possible infection, in what case treatment must be given per protocol. As mentioned before, the Rwandan guidelines include VDS algorithms that do not use risk scoring but use a pelvic examination to distinguish between mucopurulent cervical discharge and/or cervicitis (which is to be treated for CT/NG/TV) and non-muco-purulent vaginal discharge (which is to be treated for BV/TV/Candidiasis). We have decided to not take these algorithms into account.

Treatment given for:	WHO Syndromic Management	Rwandan Syndromic Management	WISH procedures	Gold standard procedures
СТ	Given with VDS and high risk / high local prevalence ¹ ; given with PID (after LAP) ²	Given with VDS and positive risk score ³ ; given with PID (after LAP) ² ; given as presumptive FSW treatment if asymptomatic ⁴	Positive for CT GeneXpert test performed after risk-scoring ⁵	Positive CT GeneXpert test (test performed on everyone)
NG	Given with VDS and high risk / high local prevalence ¹ ; given with PID (after LAP) ²	Given with VDS and positive risk score ³ ; given with PID (after LAP) ² ; given as presumptive FSW treatment if asymptomatic ⁴	Positive for NG after GeneXpert test performed after risk-scoring ⁵	Positive NG GeneXpert test (test performed on everyone)
TV	Given with VDS; covered with PID (after LAP) ²	Given with VDS no matter the risk score ³ ; covered with PID (after LAP) ² ; given as presumptive FSW treatment if asymptomatic ⁴	TV OSOM test	Positive qPCR test for Trichomonas vaginalis
UTI	NA	Treated based on reported symptoms	Positive urine dipstick test after reported symptoms ⁶	ND
BV	Given with VDS; covered with PID (after LAP) ²	Given with VDS and negative risk score ³ ; covered under VDS with positive risk score and PID (after LAP) ²	EcoCare pH swab (all pH ≥ 5.0 results treated)	Positive vaginal health qPCR DNA tool for BV ⁷

 ⁽As calculated by Log₁₀(*Lactobacillus* genus) – Log₁₀(*G. vaginalis* + *A. vaginae*). This DNA tool has a sensitivity and specificity comparable to the Nugent score. Further explained in the article by Jespers V, Crucitti T, [name] J et al. "A DNA tool for early detection of vaginal dysbiosis in African women." Res Microb 167.2 (2016): 133-41.

	on examination ⁸	or without notion of	algorithm after	
		recurrence) on	risk-scoring ⁹	
		examination		
Candidiasis	Given with VDS	Given with VDS and	Given with typical	Positive qPCR
	and typical signs	negative risk score ³	signs and	test for Candida

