- 7. If the participant reports vaginal discharge and (one of) her partner(s) has urethritis or she is positive for a risk score (2 or more positive of: age < 21; being single; 2 or more sexual partners in the past 12 months; new sexual partner in the last 3 months), the participant is to be treated for CT/NG/TV. If the participant reports vaginal discharge, none of her partners have urethritis, and she has a negative risk score (0 or 1 positive of: age < 21; being single; 2 or more sexual partners; new sexual partner in the last 3 months), the participant reports vaginal discharge, none of her partners have urethritis, and she has a negative risk score (0 or 1 positive of: age < 21; being single; 2 or more sexual partners; new sexual partner in the last 3 months), the participant is to be treated for TV/BV/candidiasis.
- 8. Under the Rwandan guidelines, presumptive treatment for CT/NG/TV is given at the STI-related first visit if the patient is an FSW, but only in the absence of symptoms. If symptomatic, the normal algorithms are followed and the presumptive treatment is not given.
- 9. Participant would have received treatment covering CT/NG if she had VDS (with or without LAP) with a positive risk score as described under (8) and/or PID, or if she was an asymptomatic FSW. Participant would have received treatment covering TV/BV if she had VDS (with or without LAP), regardless of the result of the risk score described under (7), and/or PID, or if she was an asymptomatic FSW.

Outcome /		WHO sy	/ndrom	ic man	agement		R	wanda	n syndi	romic n	nanagem	ent		WISH procedures				Gold standard		
treated for	TP1	FP ¹	FN ¹	TN ¹	Sens. ¹	Spec. ¹	TP1	FP ¹	FN ¹	TN ¹	Sens. ¹	Spec. ¹	TP1	FP ¹	FN ¹	TN ¹	Sens. ¹	Spec. ¹	Negative	Positive
N = 705	Ν	Ν	Ν	Ν	%	%	Ν	Ν	Ν	Ν	%	%	Ν	Ν	Ν	Ν	%	%	Ν	Ν
CT ²																				
NG ²																				
CT and/or NG ²																				
TV ³																				
BV ³																				
BV and/or TV ³																				
Candidiasis ⁴																				
Syphilis⁵																				
UTI ⁶																				

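### Asymptomatic sex workers count as covered for BV in SAP 5.3 and 5.4 but not in 5.1, and three row pairs in 5.3 score one Rwandan index with BV in one block and without it in the other

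*SAP*

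**What the plan says.** SAP 1.4 gives the scope of the Rwandan presumptive treatment: "all female sex workers (FSWs) without symptoms are to receive presumptive treatment for NG, CT and TV". Footnote 8 of SAP 5.3 repeats it: "presumptive treatment for CT/NG/TV is given at the STI-related first visit if the patient is an FSW". Footnote 4 to the 5.1 table and the footnotes of 5.2 name the same three infections. None of them names BV.

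The treatment table of 5.1 (it stands before 5.2) has a Rwandan column. Its CT, NG and TV rows include the sex-worker route, "given as presumptive FSW treatment if asymptomatic". Its BV row says that BV treatment is given with VDS and a negative risk score, and that BV is also "covered under VDS with positive risk score and PID (after LAP"). It has no sex-worker route.

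Two later footnotes add that route. Footnote 9 of 5.3 gives TV/BV coverage for VDS "regardless of the result of the risk score described under (7), and/or PID, or if she was an asymptomatic FSW". Footnote 3 of 5.4 ends its Rwandan BV/TV rule with "if she has PID, or if she is an asymptomatic FSW", and it is attached to the separate TV, BV, and BV and/or TV rows of the overview table. The same words stand in footnote 2 of 5.4 for CT/NG, where nothing conflicts.

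**The concern.** An analyst who codes Rwandan BV treatment from the 5.1 table leaves asymptomatic sex workers untreated for BV. One who codes it from the footnotes of 5.3 and 5.4 treats all of them. The whole group switches: VDS and PID both start from a reported symptom, so these women cannot reach BV coverage by another Rwandan route.

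The reference sets in 5.3 raise a separate problem. A reader will compare how a Rwandan index performs against WISH procedures with how it performs against the gold standard. If one reference contains BV and the other does not, part of the difference comes from the definition of the target. BV has the largest planning count of the four infections in these composites, so leaving it in or out matters. Comparing syndromic management with testing is a secondary objective, and BV is one of its named outcomes.

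**Working it through.** The plan states no accuracy or power figure that depends on this point, so there is none to reproduce. The check is a comparison of texts, followed by illustrative 2×2 arithmetic.

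**Step 1. Coverage of asymptomatic FSWs under Rwandan management.**

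| Place in SAP | CT/NG | TV | BV |
|---|---|---|---|
| 1.4 and 5.3 footnote 8 (scope of treatment) | named | named | not named |
| 5.1 table | route listed | route listed | no route listed |
| 5.3 footnote 9 | covered | covered | covered |
| 5.4 footnotes 2 and 3 | treated | treated | treated |

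**Step 2. Reference sets in 5.3 for the same Rwandan index.**

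| Index | WISH block | Gold-standard block |
|---|---|---|
| VDS, positive risk score (composite) | CT/NG + TV/BV | CT/NG + TV |
| VDS, positive risk score (vaginal infections alone) | TV/BV | TV |
| Asymptomatic FSW (composite) | CT/NG + TV/BV | CT/NG + TV |

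No single coverage rule produces both columns. If the CT/NG/TV package covers BV for both groups, the gold-standard column is out of line. If only the targeted infections count, the WISH column is. Under the 5.1 table as it stands, BV would belong in both blocks for VDS with a positive score and in neither for FSWs.

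**Step 3. Effect on the Rwandan BV row of 5.4.** Inputs: "705 participants were enrolled in the study" (SAP section 2); planning counts per 500 women, "60 cases of NG, 75 cases of CT, 75 cases of TV, 175 cases of BV" (protocol 4.3). The prevalences are NG 60/500 = 12%, CT 75/500 = 15%, TV 75/500 = 15% and BV 175/500 = 35%. The share *a* of asymptomatic FSWs is assumed.

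- BV-positive: 705 × 0.35 = 246.75. BV-negative: 458.25.
- With BV prevalence *q* among these FSWs, added true positives = 705·a·q and added false positives = 705·a·(1 − q).
- Sensitivity rises by 705·a·q / 246.75. Specificity falls by 705·a·(1 − q) / 458.25.

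| a | FSWs | Added TP, FP (q = 35%) | Change in sens., spec. | Change if q = 44% |
|---|---|---|---|---|
| 5% | 35 | 12.3, 22.9 | +5.0, −5.0 | +6.3, −4.3 |
| 10% | 70 | 24.7, 45.8 | +10.0, −10.0 | +12.6, −8.6 |
| 20% | 141 | 49.3, 91.7 | +20.0, −20.0 | +25.1, −17.2 |
| 30% | 212 | 74.0, 137.5 | +30.0, −30.0 | +37.7, −25.8 |

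Changes are in percentage points. The 44% is the higher of the two figures for high-risk women in the protocol 3.1 table; overall BV is held at 35%.

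**Step 4. Effect of the reference set** (planning prevalences, infections assumed independent).

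- TV only: 15%, or 106 of 705. TV/BV: 1 − 0.85 × 0.65 = 44.75%, or 315. Without independence, TV/BV lies between 247 (all TV within BV) and 353 (no overlap).
- CT/NG/TV: 1 − 0.85 × 0.88 × 0.85 = 36.4%, or 257. Adding BV: 1 − 0.6358 × 0.65 = 58.7%, or 414.

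An index unrelated to infection has a PPV equal to the reference-positive share. On the composite it would show about 59% in one block and 36% in the other from the definition alone. On the VDS pair without CT/NG it would show about 45% and 15%.

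**The case against.** The strongest reply is that the 5.1 BV cell is incomplete and that there is no competing rule. The table separates treatment given from infection covered. Women with VDS and a positive score are treated for CT/NG/TV, yet 5.1 already counts them as covered for BV. Asymptomatic FSWs receive treatment for the same three infections, so footnote 9 extends that logic. The dispensing table in SAP 4.1 uses shared metronidazole lines for BV and/or TV, and 5.2 reports a single TV/BV coverage category. The two footnotes that define the scored results agree with each other. The Rwandan FSW flow chart in Appendix 8.2 was not available for this review, so the content of the treatment could not be checked.

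Much of this stands. The 5.4 BV row has a definition in its own footnote, and a reader who infers that the cell is undefined goes too far. But the 5.1 row lists covered routes and still omits this one, so the text needs reconciling. The argument also does not explain the reference sets: if the package covers BV, dropping BV from the gold-standard block is the anomaly.

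Three further inferences are tempting and not supported.

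- *Every composite is affected.* Any VDS, VDS with a negative score, and the combined TV/BV treatment rows include BV in both blocks. The FSW index also has a TV-only row in each block.
- *FSW rows must be limited to asymptomatic women, and risk-score rows to women with VDS.* SAP 5.3 gives no denominator for its rows and says that it compares individual algorithms. Rows showing what one component contributes are legitimate, and a subgroup analysis would answer a different question.
- *BV is the commonest infection.* Protocol 3.1 puts HSV-2 and HPV first. BV leads only among the four infections in these composites.

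**Conclusion.** Two inconsistencies in the current SAP text are confirmed: the BV coverage of asymptomatic FSWs (5.1 against 5.3 footnote 9 and 5.4 footnote 3), and the reference sets of three row pairs in 5.3. Followed literally, 5.3 makes predictive values and sensitivity for these indices non-comparable between its blocks.

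The first could shift Rwandan BV sensitivity and specificity by about 5 to 30 points in opposite directions. That range rests entirely on the assumed 5–30% share of asymptomatic FSWs and on BV being as frequent in them as overall; unequal prevalence makes the two shifts unequal. The 36% against 59% contrast rests on planning prevalences and independence. All of these are illustrations of size, and none is a forecast of the results. The documents do not settle which coverage rule is intended.

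**What to change.** 1. Reconcile the 5.1 BV row with footnote 9 of 5.3 and footnote 3 of 5.4, so that one analysis rule for BV coverage of asymptomatic FSWs applies throughout, including the TV/BV coverage line in 5.2. Give the reason for the choice.
2. Report the Rwandan BV row and the BV and/or TV row of 5.4 under the other rule as sensitivity rows. For the combined row, also state how a woman covered for TV only is scored when she has BV only; otherwise its result remains open to interpretation.
3. In the three row pairs of 5.3, use the same infections in the WISH and gold-standard blocks: BV in both or in neither, consistent with the rule in item 1 and with what 5.1 says about VDS with a positive score. The test methods may still differ between blocks.
4. Report the number of asymptomatic FSWs beside these rows, so that readers can see how much the choice matters.

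The cost is a few lines of SAP wording, three re-specified row pairs and two sensitivity rows, all from data already collected. If these tables have already been run, the amendment should say so.
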